1.2 Disease Background

Over the past 7 years, data has emerged from numerous countries supporting the safety and efficacy of prostatic artery embolization (PAE) for the treatment of lower urinary tract symptoms (LUTS) in the setting of benign prostatic hyperplasia (BPH) (1). In response, the Food and Drug Administration (FDA) recently granted a de novo classification to Merit Medical Systems to expand the indications for Embosphere Microspheres to include PAE for the treatment of BPH. Moreover, it has given 510(k) clearances to both Embozene Microspheres and HydroPearl Microspheres.

Medication is the first line therapy for lower urinary tract symptoms (LUTS) secondary to BPH. These medications include alpha-adrenergic inhibitors, 5-alpha reductase inhibitors and phosphodiesterase inhibitors. While these medications are effective in improving urination in many men, there are also troubling side effects including retrograde ejaculation, erectile dysfunction, gynecomastia, lightheadedness, nasal congestion and loss of libido. Because of these side effects many men will discontinue the use of these medications.

It has been shown that PAE is very unlikely to result in a major complication and the minor complications tend to resolve without treatment within several weeks of the procedure. Therefore, because of its safety, and the untoward effects of BPH medications, it may be reasonable to suggest that PAE could be substituted as first line treatment for BPH. To further explore this notion, research comparing PAE to medication is needed.

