2.2 Secondary Objectives

The secondary aims are to determine if PAE will result in less adverse events compared to medication in individual patients and to determine if self assessed quality of life is better on medication or after PAE.

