3.1.3 Prostate gland measures \geq 50 grams measured by MRI, CT, or ultrasound

3.1.4 Currently taking BPH medications including either alpha blockers, 5-alpha reductase inhibitors or the combination of both for no less than 6 months

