To address the secondary aim, we will tabulate the proportion of patients AEs pre- and post-PAE, comparing the proportion using McNemar's test. A p-value <0.05 for McNemar's test will be considered evidence that the proportion of AE's differs for medication, compared to PAE. A p-value >0.05 will be considered inconclusive. We will assume that the adverse events that occur following PAE will be attributed to the procedure and not medication.

We will present the percentage of prostate infarcted at 6 months and the incidence of minor complications at 1 month descriptively, and calculate 95% confidence intervals. Post-acquisition segmentation software will be used to measure infarct volume.

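### The adverse-event comparison sets the tolerated phase of long-term medication against PAE from the procedure day onward, so its conclusion should be limited to men established on medication and drug side-effect history should be recorded at Visit 1

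*Combined protocol and SAP*

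**What the plan says.** Section 2.2 asks whether "PAE will result in less adverse events compared to medication in individual patients". Section 8.3 gives the analysis: "we will tabulate the proportion of patients AEs pre- and post-PAE, comparing the proportion using McNemar's test". The decision rule takes a p-value below 0.05 as evidence that the proportion of AEs "differs for medication, compared to PAE". A larger p-value is to be called inconclusive. Section 8.3 also states: "We will assume that the adverse events that occur following PAE will be attributed to the procedure and not medication".

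On who enters, section 3.1.4 requires "Currently taking BPH medications including either alpha blockers, 5-alpha reductase inhibitors or the combination of both for no less than 6 months". Section 1.2 gives the motive for the study: "Because of these side effects many men will discontinue the use of these medications". It then raises, in tentative terms, the idea that "PAE could be substituted as first line treatment for BPH".

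On collection, the table in 4.3 marks AE assessment at 1 day, 1 week, 3 months and 6 months, and at neither visit up to and including the procedure. The AE form in Appendix 12.2 asks about the preceding month. The medication questionnaire named in 4.1.6 and 4.3 is not reproduced.

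**The concern.** The protocol's own premise is that drug side effects drive men off treatment. The entry rule then admits only men who are still on treatment after at least 6 months. A man who stopped all BPH medication because of side effects cannot be in the medication half of the comparison. In a man who is enrolled, a one-month form cannot pick up a side effect that came early and resolved, or that was ended by changing drug.

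PAE passes through no such filter. Its early and mostly transient effects are sought from the procedure day and all charged to it. Each pair therefore compares the settled phase of one treatment with the starting phase of the other, and the plan words the conclusion as medication against PAE without restriction.

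Two things are at stake. A result against PAE could arise because the drug harms that motivated the study lie outside the observation window. A result in either direction could also be carried over to men choosing a first treatment, whom the trial does not observe.

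**Working it through.** The documents give no AE rate, sample size or power for this comparison, so there is no figure to reproduce. The 81.2% power in section 8.2 concerns IPSS only.

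**Step 1. The two halves side by side**

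| | Medication half | PAE half |
|---|---|---|
| Men | On BPH medication now and for at least 6 months (3.1.4) | Consented, eligible and treated (8.3); a pair needs both halves |
| Phase | After at least 6 months of use | Observed for several hours after PAE (4.2.1); events recorded from day 1 of study treatment (7.2) |
| Scheduled AE contacts | None marked (4.3) | 1 day, 1 week, 3 months, 6 months (4.3) |
| Recall on the form | Last month (12.2), if used before PAE | Last month (12.2), at repeated contacts |
| Attribution | Not stated | All to the procedure (8.3), although medication may continue up to the 3-month visit (4.1.4) |

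Section 8.3 does not say which post-PAE window enters McNemar's test. Section 2.3.2 lists AEs at 3 months.

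**Step 2. Direction.** What the medication half misses is early drug harm. What the PAE half includes is early PAE harm. Section 5.4 lists the commonest minor complications as rectal pain or dysuria 9.1%, acute retention 7.9% and hematuria 4.4%. Relative to men starting each treatment, this selection lowers the medication proportion and leaves the PAE proportion whole. It pushes the test against PAE.

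**Step 3. Illustration of size (assumed rates only).** Let a be the share of drug starters with an AE, d the share of those men who stop before 6 months, and c the share of men without an AE who stop. The AE share among men still on the drug is

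a(1−d) / [a(1−d) + (1−a)(1−c)].

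- a = 40%, d = 50%, c = 0: 0.20 / (0.20 + 0.60) = 25%.
- a = 40%, d = 75%, c = 0: 0.10 / (0.10 + 0.60) = 14.3%.
- Over a = 20–40%, d = 25–75%, c = 0–20%, the share runs from 5.9% (a = 20%, d = 75%, c = 0) to 38.5% (a = 40%, d = 25%, c = 20%). It is below a in every case.

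**Step 4. What that does to the test.** Assume a PAE proportion of 9.1 + 7.9 + 4.4 = 21.4% (no overlap between the three complications) and independence of a man's pre and post AEs. Use an exact two-sided McNemar test at 0.05, with 30 pairs or with 30 × 0.8 = 24 pairs (the 20% dropout in 8.2).

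| Medication AE share | Significant for PAE (24 / 30 pairs) | Significant against PAE (24 / 30 pairs) |
|---|---|---|
| 40% (all starters) | 18.0% / 24.2% | 0.0% / 0.0% |
| 25% (d = 50%) | 2.1% / 2.6% | 0.5% / 0.5% |
| 14.3% (d = 75%) | 0.1% / 0.1% | 3.8% / 5.3% |

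On these assumptions the main effect is to remove the chance of a finding in PAE's favour. A significant finding against PAE, although starters' drug harm is higher (40% against 21.4%), stays uncommon and appears mainly in the most extreme row.

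**The case against.** The strongest reply is that the aim is worded within individual patients. For a man established on medication, his present side-effect burden is the relevant comparator, and selection of tolerant men does not understate it. First-line use is a tentative remark in the background, and no objective or hypothesis concerns men starting medication. This stands, and it is why the remedy is to state the population rather than to redesign the comparison. It does not remove the mismatch of phases within each enrolled man, and sections 2.2 and 8.3 do not state the restriction.

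A reader might go further than the documents allow in four ways.

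- That the comparison cannot support a finding of fewer AEs with PAE. The selection runs the other way, so a significant result favouring PAE would be conservative with respect to it. Fewer AEs is also a question the study asks, and the planned conclusion is only that the proportions differ.
- That a null result would show PAE to be no safer. Section 8.3 already calls a p-value above 0.05 inconclusive.
- That every man who stopped a drug early is excluded. Section 3.1.4 does not require the same drug throughout, so a man who switched can enter. Only men who stopped all medication are shut out, along with the events that fell outside the recall month.
- That the medication figure is too low by a known number of points. No drug AE or discontinuation rate is given. Men unhappy with their medication may also be more likely to enrol, which would raise the pre-PAE proportion.

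The unseen medication questionnaire may already ask about stopped or changed drugs. If it does, part of the fix is in place.

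**Conclusion.** The concern holds in a limited form. The plan compares AEs on established, tolerated medication with all AEs from the procedure day onward in evaluable PAE-treated men. It does not acknowledge the asymmetry, and it schedules no pre-PAE AE assessment to supply the medication half.

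With respect to this selection the bias is against PAE. A significant result in PAE's favour could stand, as far as this bias goes. A significant result against PAE could not be interpreted, nor could any extension to men starting medication.

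Net direction and size are unknown. The 5.9% to 38.5% range and the test probabilities rest wholly on assumed AE and stopping rates, the three summed complication rates and independence within pairs. They show that the effect could matter, not how large it is. This is a point about data collection and the wording of a secondary aim. It leaves the primary IPSS analysis untouched.

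**What to change.** 1. In sections 2.2 and 8.3, state that the AE comparison and its conclusion apply to men established on BPH medication for at least 6 months, and that they do not estimate the harm of starting medication.
2. At Visit 1, using the questionnaires already planned, record current side effects on medication, side effects at any time since BPH medication was started, and any BPH drug stopped or changed because of side effects. Mark this in the 4.3 table, so that the pre-PAE half of McNemar's test has a defined source.
3. Report the since-start proportion descriptively beside the on-drug and post-PAE proportions, stating the observation window of each. Keep it out of McNemar's test.

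The cost is protocol and SAP wording and a few questions at an existing visit. Eligibility, treatment, visits and sample size do not change. There are four downsides. The since-start answers rest on longer recall. Their window can exceed the PAE window, which would tilt that contrast towards PAE and is the reason to keep it descriptive. Men who stopped all medication remain unobserved. The safety claim becomes narrower.

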2.3.2 Secondary Study Outcome Variable

1. Improvement of QoL score at 6 months
2. Improvement of uroflowmetry (Qmax, PVR) at 6 months
3. Reduction of prostate volume at 6 months
4. Percentage of prostate infarcted at 6 months
5. Incidence of adverse events at 3 months

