4.0 STUDY PLAN

4.1 Study Procedures

4.1.1 Study Design

This will be a single arm, non-blinded study of PAE in a small population with BPH to determine if PAE is as effective as medication (non-inferiority) in reducing urinary symptoms due to BPH. After IRB approval of a written informed consent and over approximately a 24 month duration, a total of N=30 subjects will be recruited at 3 sites. Only subjects \geq 40 years will be screened for study recruitment. Clinical procedures and evaluations will consist of a preoperative screening assessment to determine if the potential study subject meets the inclusion and exclusion criteria, enrollment, surgical procedure for prostatic artery embolization (PAE), and follow-up visits at 24 hours, 1 week, 3, 6, & 12 months. An MRI will be performed after the 6-month visit in those patients who underwent embolization to detect a change in prostatic volume and perfusion and to exclude complication.

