4.1.8 Visit 3 -1 Day Follow-up

Subjects will be seen in clinic or contacted by phone or by teleconference, per the subject's preference, the day following PAE procedure (+3 days). As most

complications of the procedure will be evident within this time, this visit is to evaluate for early AEs. If an AE is suspected based on change in pain scores or functionality, an appropriate work-up will be performed which may include MRI or CT.

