4.1.9 Visit 4 -1 Week Follow-up

Subjects will be seen in clinic or contacted by phone or by teleconference, per the subject's preference, one week following PAE procedure (+5 days). As most complications of the procedure will be evident within this time, this visit is to evaluate for early AEs. If an AE is suspected based on change in pain scores or functionality, an appropriate work-up will be performed which may include MRI or CT.

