4.1.10 Visit 5 - 3 Month Follow-Up

Subjects will return 90 +/- 14 days after PAE procedure to complete IPSS, and QOL questionnaires; to have Qmax and PVR measured; medication history questionnaires will be completed; and subjects will be evaluated for possible adverse events. It will be recorded if subjects are unable to hold medications at this time due to residual urinary symptoms. If an AE is suspected based on change in pain scores or functionality, an appropriate work-up will be performed.

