4.3 Time and Events Table

	Visit 1 (Screening)	Visit 2 (Procedure)	Visit 3 (1 Day)	Visit 4 (1 week)	Visit 5 (3 month)	Visit 6 (6 Month)	Visit 7 (12 month)
Informed Consent	X						
MRI	X					X	
PAE procedure		X					
IPSS w/QOL	X				X	X	X
Qmax	X				X	X	X
PVR	X				X	X	X
Medication History Questionnaire	X	X			X	X	
AE Assessment			X	X	X	X	

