12.2 Adverse Event Questionnaires

Prostatic Artery Embolization Study

IRB#

PI:

Subject ID #: _____

Date of Visit: _____

Adverse Event

Have you experienced any of the following symptoms within the last month?

(Check all that apply)

- Nasal congestion
- Light headedness
- Retrograde ejaculation (Dry ejaculation)
- Priapism (Painful erection lasting 4 or more hours)
- Fatigue or weakness
- Headaches
- Hypotension (Low blood pressure)
- Heart fibrillation or Chest pain
- Swelling in hands, feet, or ankles
- Nausea
- Dizziness
- Fainting
- Erectile dysfunction
- Lower sex drive
- Gynecomastia (Male breast tissue)
- Dysuria (Burning with urination)
- Blood in Urine
- Blood in stool
- Blood in sperm
- Sores on penis
- Sores on buttocks

Form Completed By: _____

Signature

Date

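### Section 8.3 estimates minor complications at 1 month, where no contact is scheduled; no analysis is tied to the listed 3-month AE outcome, and the one-month-recall form does not reach about days 7-60

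*Combined protocol and SAP*

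**What the plan says.** Section 2.3.2 lists, as the fifth secondary outcome, "Incidence of adverse events at 3 months". In section 8.3 the descriptive safety estimate is "the incidence of minor complications at 1 month descriptively", with 95% confidence intervals. The paragraph before it tabulates the proportion of patients with AEs before and after PAE and compares them by McNemar's test, without saying which post-PAE period counts.

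Section 4.1.1 plans "follow-up visits at 24 hours, 1 week, 3, 6, & 12 months". In the table in 4.3, the row "AE Assessment" is marked at 1 day, 1 week, 3 months and 6 months, and there is no 1-month column. The 1-week contact is "one week following PAE procedure (+5 days" allowed (4.1.9). For the 3-month visit, "Subjects will return 90 +/- 14 days after PAE procedure" (4.1.10). The single AE form in Appendix 12.2 asks: "Have you experienced any of the following symptoms within the last month".

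Other routes for AE data exist. Section 4.1.10 has subjects evaluated for AEs at Visit 5 with no stated look-back limit. Sections 4.1.7 and 4.2.1 give subjects numbers to call. Section 7.2 asks for non-serious AEs to be documented at least monthly, with onset and resolution dates, through a 30-day follow-up period.

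**The concern.** The planned estimate and the listed outcome differ in three ways: the time point (1 month against 3 months), the term (complications against adverse events) and the scope (minor only against all). Followed as written, 8.3 yields a figure for a time at which nobody is scheduled to be contacted, and leaves the listed 3-month outcome without an analysis of its own.

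The form adds a second problem. A one-month look-back from a 3-month visit does not join up with the 1-week contact. Section 1.2 says that minor complications tend to resolve within several weeks of the procedure. An event that starts after the first week and is over by about day 60 is therefore of the kind the study expects, and the structured question would not reach it. Comparing AEs on medication with AEs after PAE is a secondary objective (2.2), so how post-PAE events are collected matters to a stated aim.

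**Working it through.** The plan gives no figure of its own to reproduce here, so the check is interval arithmetic on the visit schedule.

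**Inputs.** 1-week contact: day 7 to 12 (4.1.9). 3-month visit: day 76 to 104, nominally 90 (4.1.10). Recall: the last month (12.2), taken as 30 days. I assume that the 12.2 form is the instrument used at the AE assessments; the documents do not say at which visits it is completed.

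**Days outside the form's reach** = (3-month visit day - 30) - 1-week contact day. Share = that number / 3-month visit day.

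| 1-week contact | 3-month visit | Not reached | Days | Share |
|---|---|---|---|---|
| day 7 | day 90 (nominal) | 7-60 | 53 | 59% |
| day 12 | day 90 | 12-60 | 48 | 53% |
| day 7 | day 76 | 7-46 | 39 | 51% |
| day 12 | day 76 | 12-46 | 34 | 45% |
| day 7 | day 104 | 7-74 | 67 | 64% |
| day 12 | day 104 | 12-74 | 62 | 60% |

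With recall of 28 or 31 days, the nominal result is 55/90 = 61% or 52/90 = 58%.

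**The 1-month estimate.** After the 1-week contact, 30 - 7 = 23 of the first 30 days (77%) remain; with contact on day 12, 30 - 12 = 18 of 30 (60%). The 3-month form does not recover them: even the earliest visit reaches back only to day 76 - 30 = 46.

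**If 7.2 is carried out to day 30.** The nominal gap becomes days 30-60: 30/90 = 33%.

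**Days are not events.** The 59% is a share of time. Sections 4.1.8 and 4.1.9 say most complications are evident early. Suppose 80-90% of events start in the first week (an assumption; the documents give no figure) and the rest are spread evenly over the remaining 83 days. The share starting in the gap is then (10% to 20%) x 53/83 = 6% to 13%. Events that persist past day 60 would still be picked up, and so would those reported by another route, so fewer than this would be missed.

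**The case against.** The strongest reply is that the 12.2 form is not declared to be the only source of AE data. The AE evaluation at Visit 5 is open-ended, 7.2 requires dated AE records, and subjects can call in. With onset dates, a 1-month incidence can be worked out at a later visit, and the 30-day period in 7.2 may be where the 1-month time point comes from.

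This stands in part. It rules out a conclusion that a reader might draw from the form, that symptoms between days 7 and 60 are never asked about. It does not close the gap. Section 7 is headed for drugs and contrast agents, 7.2 schedules no contact, the telephone lines rely on the subject to report, and nothing tells the Visit 5 assessor to ask back to the 1-week contact.

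Three other inferences are tempting and not supported:

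- That only minor complications are analysed. The McNemar comparison is not restricted to minor events, 9.3.1 has all AEs summarised for publication, and 8.1 has a stopping rule on major complications. What is missing is a descriptive estimate with an interval that includes major events and is tied to 3 months.
- That more than half the window is always outside the form. With contact on day 12 and the visit on day 76 it is 45%.
- That the gap favours PAE. Missed post-PAE events would do so. But 8.3 attributes every post-PAE AE to the procedure, although medication need only stop by the 3-month visit (4.1.4), and 4.3 marks no AE assessment at screening. Both of these work against PAE.

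**Conclusion.** The point holds as a mismatch between outcome, analysis and data collection. The 8.3 estimate is not the outcome in 2.3.2, it is set at a time with no scheduled contact, and no analysis is explicitly tied to AEs at 3 months. On the nominal schedule the form does not reach 53 of 90 days (59%; about 45-64% across the visit windows with 30-day recall), or about 33% if 7.2 is carried out to day 30. Cumulative 3-month incidence may therefore be undercounted. By how much depends on when events start, how long they last and how well the other routes work, none of which the documents quantify. The net direction of any bias in the pre/post comparison cannot be determined from the documents. This affects a secondary outcome, not the primary IPSS analysis, and it should be put right because the repair is simple.

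**What to change.** 1. In 8.3, replace the 1-month minor-complication estimate with *all adverse events, minor and major, from PAE through the 3-month visit*, with 95% confidence intervals, so that it matches 2.3.2.
2. On the post-PAE form in 12.2, add an item covering the time *since your last study visit*, with an onset date. This makes the 3-month figure cumulative and supplies the onset dates that 7.2 already asks for.
3. Keep the last-month item, so that windows of equal length before and after PAE can be compared, and state in 8.3 which post-PAE window the McNemar comparison uses.

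The cost is a change of wording in 8.3 and one extra item with a date column on a one-page form; no visit is added. The drawback is that recall over up to 3 months is less exact than over one month.

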9.0 STUDY MANAGEMENT

9.1 Institutional Review Board (IRB) Approval and Consent

It is expected that the IRB will have the proper representation and function in accordance with federally mandated regulations. The IRB should approve the consent form and protocol.

In obtaining and documenting informed consent, the investigator should comply with the applicable regulatory requirement(s), and should adhere to Good Clinical Practice (GCP) and to ethical principles that have their origin in the Declaration of Helsinki.

Before recruitment and enrollment onto this study, the patient will be given a full explanation of the study and will be given the opportunity to review the consent form. Each consent form must include all the relevant elements currently required by the FDA Regulations and local or state regulations. Once this essential information has been provided to the patient and the investigator is assured that the patient understands the implications of participating in the study, the patient will be asked to give consent to participate in the study by signing an IRB-approved consent form.

Prior to a patient's participation in the trial, the written informed consent form should be signed and personally dated by the patient and by the person who conducted the informed consent discussion.

